17.3 Reporting to Regulatory Authorities / IRBs / ECs / REBs / Investigators

In addition to those events defined in Section 17.6 of Phase 1 of the ADVANTAGE AF study, BSC is responsible for reporting adverse event information to all participating Principal Investigators, IRBs / ECs / REBs and regulatory authorities, as applicable. Sponsor reporting to the FDA will adhere to applicable requirements, including 10 working days following Sponsor awareness for occurrence of ST elevation or clinical signs of ischemia or injury for those subjects receiving treatment for CTI-mediated AFL with the FARAPPOINT Catheter as a component of the FARAPULSE PFA System.

18 Informed Consent

Informed consent requirements remain the same as Phase 1 of the ADVANTAGE AF study and can be referenced **Section 18** of the Phase 1 clinical investigational plan.

19 Committees

The safety monitoring operations team, clinical events committee, data monitoring committee and executive steering committee will operate in the same manner for Phase 2 of the ADVANTAGE AF study as defined in Phase 1. Refer to **Section 19** of the Phase 1 clinical investigational plan for additional information.

20 Suspension or Termination

Suspension and termination requirements remain the same as Phase 1 of the ADVANTAGE AF study and can be referenced in **Section 20** of the Phase 1 clinical investigational plan.

21 Study Registration and Results

Study registration and results requirements remain the same as Phase 1 of the ADVANTAGE AF study and can be referenced in **Section 21** of the Phase 1 clinical investigational plan.

22 Reimbursement and Compensation for Subjects

Reimbursement and subject compensation requirements remain the same as Phase 1 of the ADVANTAGE AF study and can be referenced in **Section 22** of the Phase 1 clinical investigational plan.

23 Abbreviations and Definitions

23.1 Abbreviations and Acronyms

Table 23.1-1: Abbreviations and Acronyms

3D	Three dimensional
AAD	Antiarrhythmic drug
ACL	Arrhythmia Core Laboratory
ACT	Activated clotting time
ADE	Adverse Device Effect
AE	Adverse event
AF	Atrial fibrillation
AFEQT	Atrial Fibrillation Effect on QualiTy-of-Life Questionnaire
AFL	Atrial flutter
AT	Atrial tachycardia
AVNRT	Atrioventricular nodal reentrant tachycardia
BDB	Bidirectional block
BMI	Body Mass Index
BSC	Boston Scientific Corporation (Sponsor)
BUN	Blood urea nitrogen
CBA	Cryoballoon ablation
CEC	Clinical Events Committee
CHA ₂ DS ₂ -VASc	A clinical prediction rule for stroke
CHF	Congestive heart failure
CICL	Cardiac Imaging Core Laboratory
CIP	Clinical Investigation Plan (synonymous with study protocol)
COVID-19	COrona VIrus Disease 2019: an illness caused by SARS-CoV-2
CPS	Chronic Procedural Success
CRF	Includes CRF (case report form) and eCRF (electronic CRF)
CT	Computed tomography
CTI	Cavo-tricuspid isthmus
CXR	Chest X-ray
DOAC	Direct oral anticoagulant
DW, DWI	Diffusion weighted, Diffusion weighted image

ECG	Electrocardiogram
eCRF	Electronic case report form
eGFR	Estimated glomerular filtration rate
EM	Event monitor (any of several hardware modalities)
EQ-5D-3L	The 3-level EuroQol standardized questionnaire of health states
FDA	Food and Drug Administration
HCP	Health care personnel
HCT	Hematocrit
HGB	Hemoglobin
Holter	Holter monitor
ICE	Intracardiac echocardiography
ICF	Informed consent form
INR	International normalized ratio
IRB / EC / REB	Institutional Review Board / Ethics Committee / Research Ethics Board
IRE	Irreversible electroporation
ITT	Intent(ion)-to-Treat
IVC	Inferior vena cava
LA	Left atrium or left atrial
LAPW	Left atrial posterior wall
LBBB	Left bundle branch block
LTFU	Lost-to-follow-up
MITT	Modified Intent(ion)-to-Treat
MRI	Magnetic resonance imaging
NIHSS	National Institutes of Health Stroke Scale
NYHA	New York Heart Association
PAF	Paroxysmal atrial fibrillation
PersAF	Persistent atrial fibrillation
PFA	Pulsed field ablation
PP	Per Protocol
PV	Pulmonary vein
PVI	Pulmonary vein isolation
PW	Posterior wall
PWI	Posterior wall isolation
RFA	Radiofrequency ablation
SADE	Serious Adverse Device Effect
SAE	Serious adverse event
SOC	Standard of care
TEE	Transesophageal echocardiography
TIA	Transient ischemic attack
TSF	Technical Source Form (see Section 10.3 of ADVANTAGE AF – Phase 1 protocol)
TTE	Transthoracic echocardiography
UADE	Unanticipated Adverse Device Effect

23.2 Definitions

Protocol terms not otherwise defined in the protocol are defined in **Table 23.2-1**:

Table 23.2-1: Definitions

Term	Definition
AF, AFL, and AT Burden	The proportion of time spent in atrial arrhythmia determined by the ratio of the total duration of LUX-Dx detected AF and AT episodes adjudicated as true AF, AFL, or AT divided by the total follow-up duration less the duration of AF and AT episodes without a stored ECG to analyze. Adjudication of episodes will be described in the Statistical Analysis Plan.
Acute Procedural Success	Defined in Section 3.4.1 .
Antiarrhythmic Drugs, Class I and III	
Class I / III AADs are those pharmaceutical agents approved or used in the relevant jurisdiction for the treatment of cardiac arrhythmia. For the ADVANTAGE AF Study, Class I and III AADs include but are not limited to:
 
 • Class I, sodium channel blockers: disopyramide, flecainide, procainamide, propafenone, quinidine. • Class III, potassium channel blockers: amiodarone, dofetilide, dronedarone, sotalol. 
Should other Class I or III AADs become approved or used in the relevant jurisdiction for the treatment of cardiac arrhythmia during the ADVANTAGE AF Study, they will be considered as Class I / III AADs for this protocol.

Attempt Subjects	Attempt Subjects are defined in Section 6.6.4 of ADVANTAGE Phase 1 protocol.
BeatLogic	The BeatLogic Core Lab Adjudicator Tool (Adjudicator Tool) is a software component (ECG Classification system) of the BodyGuardian Remote Monitoring System (BGRMS; K192732). The BeatLogic software component detects and identifies various rhythms. The Adjudicator Tool applies the BeatLogic software algorithm to ECGs recorded by the LUX-Dx Insertable Cardiac Monitor (ICM) and classifies each episode as atrial arrhythmia or non-atrial arrhythmia.

Term	Definition
Blanking Period	
An interval in which recurrent AF, AFL or AT, cardioversion or a first re-ablation do not constitute Treatment Failure beginning on Day 0 and running for 90 days thereafter.
 
 • The Blanking Period has no impact on the assessment of AEs. • For subjects with only an Index Procedure, the Blanking Period will be Day 0 to Day 90 inclusive. • For subjects who require a Rescheduled Index Procedure, the Blanking Period will be the Study Day of the Rescheduled Index Procedure (Day 0) plus 90 days inclusive • For subjects treated with a Non-Failed AAD during the Blanking Period, a Treatment Failure due to the use of that drug only occurs if there is continued use of that drug following the earlier of either the Day 90 visit or Day 104.
(Persistent AF) Chronic Success	Defined in Section 3.4.2.
Composite Serious Adverse Events	Composite Serious Adverse Events are defined in Section 3.3.
COVID-19 Related Disruptions	A disruption to any study procedure resulting directly or indirectly from the COVID 19 pandemic, including but not limited to subject illness, study site restrictions and limitations, shipping / manufacturing interruptions, significant changes in regulatory guidance and / or governmental restrictions on travel, association, and the prioritization of healthcare resources.
Dates	
 • Consent Date: The date a subject signs the ICF. • Exit Date: The date on which a subject's study participation ends. • Onset Date: The date on which a condition or AE begins. • Start Date: Day 0, the date of the Index Procedure or Rescheduled Index Procedure
Day (or Study Day)	A Day is an enumerated day of follow-up that begins on an Enrolled Subject's Start Date (Day 0).

Term	Definition
Detectable AF, AFL, or AT	
Detectable AF, AFL or AT is an episode of AF, AFL or AT which:
 
 • Is recorded for review on a LUX-Dx ICM and meets any of the following criteria: 
 ○ Adjudicated symptomatic (patient initiated) recording that contains ≥ 30 seconds of continuous atrial arrhythmia. ○ Adjudicated AF or AT episode captured by LUX-Dx that contains at least 30 seconds of atrial arrhythmia and overlaps a simulated bi-monthly, 2 minute event monitor transmission period. ○ Adjudicated AF or AT episode captured by LUX-Dx that contains at least 30 seconds of atrial arrhythmia and overlaps a simulated 24 hour holter period occurring the day before the Day 180 and Day 360 Assessments (or last day of respective visit window if visit(s) is missed)⁸. • Continuous AF, AFL or AT for the entirety of a 12 lead ECG if the continuous interpretable signal is 10 seconds or longer • Exclusions: 
 ○ CTI isthmus-dependent AFL if the subject did not have a CTI ablation with the FARAPoint PFA Catheter ○ Arrhythmias recorded on other devices, including implantable monitors and consumer wearables, not specified in the ADVANTAGE AF Study procedures
Failed AAD	
Failed AADs include any and all Class I / III AAD determined at the time of enrollment to have been failed for effectiveness or intolerance. Failed AADs do not include Class I / III AADs determined at the time of enrollment solely to be contraindicated.
 
Failed AADs must be established as part of the Baseline Assessment for agent, type of failure (arrhythmia recurrence or AAD intolerance) and the maximum failed dose (the total daily dose at which such failure occurred).

Intent Subjects	
Intent Subjects are defined in Section 6.6.3 of the ADVANTAGE Phase 1 Protocol.

Non-Failed AAD	
A Non-Failed AAD is:
 
 • Any Class I / III AAD not established at the Baseline Assessment as a Failed AAD • Any Failed AAD used after Day 90 at a daily dose exceeding the maximum failed dose established at the Baseline Assessment

⁸ Day prior to the Day 180 and Day 360 visits was selected to prevent overlap in the rhythm captured by the visit-required 12-lead ECG.

Term	Definition
Persistent atrial fibrillation	PersAF is defined as continuous AF that is sustained beyond 7 days, but not greater than 12 months duration.
Pulmonary vein dimensions	
For the purpose of assessing potential PV stenosis:
 
 • PV dimensions will be measured in two roughly orthogonal diameters approximating the longest and shortest diameters at the plane of measurement. • The measured PV diameter is defined as the geometric mean of these 2 measurements. • The PV cross-sectional area is computed using the formula for area of an ellipse, where the longest and shortest axis measurements of the PV diameter serve as the major and minor axes of the ellipse, using half of each axis diameter as the radii for calculation.
Roll-In Subjects	Roll-In Subjects are defined in Section 4.1.1 , Section 4.2 and ADVANTAGE Phase 1 Protocol Section 6.6.2 .
Severe COVID-19 Subjects	
Any study subject who contracts COVID-19 infection during study participation that:
 
 • Requires supplemental oxygen, positive pressure ventilation, and / or intubation OR • Is associated with any medically serious sequelae of COVID 19, including but not limited to new onset cardiac arrhythmia, heart failure, myocarditis, neurologic dysfunction or other organ dysfunction, or thromboembolic disease. 
Such subjects will be initially defined by the Investigator and confirmed by the CEC. The Onset Date will be the date of symptom onset in a subsequently clinically confirmed case of COVID-19 infection.

Source data Ref: ISO 14155	All information in original records, certified copies of original records of clinical findings, observations, or other activities in a clinical investigation, necessary for the reconstruction and evaluation of the clinical investigation. This includes source data initially recorded in an electronic format.
Source document Ref: ISO 14155	Original or certified copy of printed, optical, or electronic document containing source data, including TSFs.
Treatment Failure	Treatment Failure is the absence of Treatment Success due to one or more protocol-stipulated reasons.
Treatment Subjects	Treatment Subjects are defined in Section 6.6.5 of the ADVANTAGE Phase 1 Protocol.
Treatment Success	Treatment Success is defined in Section 3.4

Term	Definition

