Treatment Success as defined in **Section 3.4** but counting subjects with any re-ablation for AF, AFL, or AT as Treatment Failures

- **Off Drug Treatment Success**

Treatment Success as defined in **Section 3.4** but counting subjects treated with any Class I / III AAD after Day 90 as Treatment Failures

- **Re-Ablation Rate**

Defined as the proportion of subjects who receive one or more re-ablations during study follow-up for AF, AFL, or AT, at any time during follow-up, and subdivided by re-ablation during Days 0 – 90 and by Days 91 and thereafter. CTI only re-ablation is excluded for subjects who did not receive CTI ablation with the FARAPPOINT catheter.

- **AF, AFL, and AT Burden**

Descriptive statistics on AF, AFL, and AT burden, as defined in Section 23.2 and assessed during the observation period from Day 91 to Day 360 Assessment. AF, AFL, and AT burden will also be calculated for the days from LUX-Dx activation to the Index/ Rescheduled Index Procedure (up to 30 days pre-procedure) and compared to the burden calculated from Day 91 to Day 360 Assessment. Additionally, AF, AFL, and AT burden statistics from Day 91 to Day 360

will be stratified by recurrence based on LUX-Dx detected AF, AFL, or AT using various episode duration thresholds.

- **Healthcare Utilization by AF, AFL, and AT Burden**

Healthcare utilization, defined by outcomes of all-cause hospitalization, cardioversion for AF, AFL, or AT recurrence outside of an ablation procedure, re-ablation for AF, AFL, or AT and unscheduled cardiovascular follow-up assessments, will be compared between subjects grouped by AF, AFL, and AT burden from Day 91 to Day 360 Assessment. Burden groups will include rates of 0%, 0-0.1%, 0.1-1%, 1-5%, 5-10%, and >10% AF, AFL, and AT burden.

- **Healthcare Utilization by AF, AFL, or AT Recurrence Duration**

Healthcare utilization, defined by outcomes of all-cause hospitalization, cardioversion for AF, AFL, or AT recurrence outside of an ablation procedure, re-ablation for AF, AFL, or AT and unscheduled cardiovascular follow-up assessments will be compared between subjects grouped by longest duration of AF, AFL, or AT captured by LUX-Dx (based on continuous monitoring) between Day 91 and Day 360 Assessment. Groups will include no recurrence and longest duration of 0-6 minutes, 6 minutes – 1 hour, 1-6 hours, 6-24 hours, and \geq 24 hours.

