Inclusion Criteria:

1. Subjects enrolled in Phase 2 of the ADVANTAGE AF study with an active LUX-Dx ICM device.

Exclusion Criteria:

None

Sub-Study Procedures

No additional study procedures or follow-up assessments are required for subjects that agree to participate in the LUX-Dx sub-study. The LUX-Dx ICM device will continue to be programmed as defined within the ADVANTAGE AF Phase 2 protocol or as determined most appropriate to assess the subjects' heart condition per physician assessment. Subjects will continue to use their myLUX patient application to complete manual transmissions when experiencing symptoms and remain connected to the LATITUDE Clarity™ system throughout the duration of the trial.

Data Collection and Analysis

Once a LUX-Dx subject completes their Day 360 assessment, they will continue to be remotely monitored via LATITUDE Clarity for up to a total of 3 years (36 months) from the ADVANTAGE AF index ablation procedure. There is no additional data collection that will need to be entered in the study database after the Day 360 assessment.

Subjects will need to maintain connection between their device and the myLUX patient app to ensure continuous arrhythmia monitoring. It is recommended that subjects do not stay disconnected for more than two (2) weeks to ensure no data is overwritten.

No additional study procedures or follow-up assessments are required for subjects that agree to participate in the LUX-Dx sub-study, however, participating subject's electronic medical records or health care claims may be reviewed to assess for clinical events associated with ablation efficacy (e.g., cardioversions, re-ablations, hospitalizations).

Adverse events will not be reported through the clinical study database after the subject completes their active participation (i.e., Day 360 assessment visit) in Phase 2 of the

ADVANTAGE AF Study. Adverse events will be reported through normal commercial channels/complaint processes as applicable by sites.

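### The Phase 2 burden definition counts time the LUX-Dx did not record as arrhythmia-free, which biases AF/AFL/AT burden downward

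*Combined protocol and SAP*

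**What the plan says.** Appendix A 23.2 gives the numerator of burden as the "total duration of LUX-Dx detected AF and AT episodes adjudicated as true AF, AFL, or AT". This is "divided by the total follow-up duration less the duration of AF and AT episodes without a stored ECG to analyze". The definition leaves one matter to the SAP: "Adjudication of episodes will be described in the Statistical Analysis Plan". The denominator is not deferred.

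Appendix A 3.5.2 sets two periods. Post-ablation burden is "assessed during the observation period from Day 91 to Day 360 Assessment". Pre-procedure burden is "calculated for the days from LUX-Dx activation to the Index/ Rescheduled Index Procedure (up to 30 days pre-procedure"), and the two are compared. The post-ablation value also sorts subjects into groups of 0%, 0-0.1%, 0.1-1%, 1-5%, 5-10% and >10% for the Healthcare Utilization comparison.

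On recording:

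- Sections 8.1.2.3 and 8.2.1 require an established LATITUDE Clarity connection by the end of the effectiveness evaluation period. They set no minimum recorded time.
- Section 7.6 has sites contact subjects who are disconnected for more than 7 days. It does not say how the gap is treated in analysis.
- Appendix B adds: "It is recommended that subjects do not stay disconnected for more than two (2) weeks to ensure no data is overwritten".

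**The concern.** A monitor can contribute arrhythmia time only while it is active and its data can be retrieved. Section 23.2 already removes detected episodes that cannot be adjudicated because no ECG was stored. It does not remove time in which nothing could have been detected, or in which what was detected has been lost. That time is treated as observed and free of arrhythmia.

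Two uses of burden are exposed. First, subjects can fall into a lower Healthcare Utilization group because of incomplete recording. Second, the before/after comparison is uneven. The pre-procedure window opens at device activation, so time before the device was active is excluded by construction. Day 91 to the Day 360 Assessment is calendar time whether or not the device was active. Device-inactive time can therefore lower only the post-ablation value, which flatters the apparent reduction. Data lost after activation could affect either window.

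Appendix A 1.4 names burden as something Phase 2 will evaluate to inform the design of future studies, and characterizing it is an Appendix B objective.

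**Working it through.** The documents state no burden figure, so there is nothing to reproduce. The check is direct ratio arithmetic.

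**Inputs**

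- Period T: Day 91 to Day 360 inclusive, 360 − 91 + 1 = 270 days. With the ±30-day visit window, 240 to 300 days (3.5.2, 7.13).
- Lost days u: not given in the documents. Assumed 7, 14, 30 and 60.
- Cut points: 0, 0.1, 1, 5 and 10% (3.5.2).
- Episodes without a stored ECG: set to zero here, because 23.2 already handles them.

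**Formula.** Let A be adjudicated arrhythmia time in the recorded T − u days. Burden over recorded time is A/(T − u). Section 23.2, applied to the same period, gives A/T. The ratio of the two is

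factor = (T − u)/T.

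**Results, T = 270**

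| Lost days | Factor | 12% reads | 11% reads | 5.5% reads | 1.1% reads |
|---|---|---|---|---|---|
| 7 | 263/270 = 0.974 | 11.69% | 10.71% | 5.36% | 1.07% |
| 14 | 256/270 = 0.948 | 11.38% | 10.43% | 5.21% | 1.04% |
| 30 | 240/270 = 0.889 | 10.67% | 9.78% | 4.89% | 0.98% |
| 60 | 210/270 = 0.778 | 9.33% | 8.56% | 4.28% | 0.86% |

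At 30 lost days, burdens of 11%, 5.5% and 1.1% each drop one group; 12% does not. At 60 days, 12% drops as well. Over the visit window, 30 lost days give 210/240 = 0.875 to 270/300 = 0.900.

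Short gaps matter only near a cut point. For the 10% cut, 7 lost days move a subject only if burden over recorded time is at most 10/0.974 = 10.27%. For 14 days the limit is 10/0.948 = 10.55%.

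The 0% group behaves differently. A subject with little recording and no detected arrhythmia reads 0% under any denominator. Only a report of recorded days would show how little stands behind that value.

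**The case against.** The strongest reply is that the protocol works to keep recording complete. Insertion is required within 7 days of the procedure (7.6), so there are 91 − 7 = 84 days to settle connection before the post-ablation period opens. Sites confirm transmissions at Day 7 if available and at every scheduled visit from Day 30. Disconnection beyond 7 days triggers contact. A device with under one year of estimated longevity is excluded (5.3). This stands as a reason to expect small gaps in most subjects. It does not define how a gap is treated when one occurs.

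Second, a reader might infer that a subject first connected on Day 120 or Day 180 has lost everything before that day. The documents do not support this. The LUX-Dx stores S-ECGs in its own memory (2.3.1), so late or interrupted connection does not by itself mean lost data. The overwriting remark comes from the optional sub-study and does not say what is overwritten. If an episode is still logged but its ECG is gone, 23.2 already subtracts its time.

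Third, a reader might infer that days outside the period also dilute burden. Follow-up is counted from Day 0 ("A Day is an enumerated day of follow-up that begins on an Enrolled Subject's Start Date (Day 0"), so a literal reading would put a Day 91-360 numerator over the whole year (270/360, a 25% understatement), or 30 pre-procedure days over the year (30/360, a 92% understatement). That is not the plan's rule. Section 3.5.2 fixes both periods, and the natural reading applies them to numerator and denominator alike. What remains is an ambiguity: total follow-up, counted from Day 0, does not fit a window that ends at the procedure.

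Finally, burden is an additional endpoint, analyzed descriptively, and no hypothesis is tested on it. That is correct and limits the importance of the point.

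**Conclusion.** The point holds as a minor correction. As written, 23.2 leaves unrecorded time within the assessed period in the denominator, and the effect on burden can only be downward. The factor is 0.974 to 0.778 for 7 to 60 lost days of 270. Gaps of a month or more can shift subjects by a group; gaps of one or two weeks matter only close to a cut point.

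Three assumptions underlie these sizes. The lost days are assumed, since the documents give no recording rate. The factor compares 23.2 with burden over recorded time; it equals the understatement of true burden only if arrhythmia is as frequent in lost time as in recorded time. The Phase 2 SAP is not among the documents, so whether it restates the denominator cannot be checked; 23.2 refers only adjudication to it.

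Neither the 25% and 92% figures nor an equation of late connection with lost recording forms part of this conclusion. The primary endpoints and sample size are unaffected.

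**What to change.** In Appendix A 23.2 and the Phase 2 SAP, define the denominator as LUX-Dx-recorded time within the period assessed (device active and data retrieved), less the duration of AF and AT episodes without a stored ECG. Limit the numerator to the same period. State that time with late or interrupted connection counts as recorded if its data were later recovered.

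Apply this one definition to the pre-procedure window, to Day 91 through the Day 360 Assessment, and to Appendix B. It also removes the poor fit between total follow-up and the pre-procedure window. Report recorded days per subject alongside each burden summary.

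The cost is one clause, plus use of device-activation and LATITUDE data-retrieval records the sponsor already holds. The drawback is noisier burden values for subjects with little recorded time, which the reported recorded days would make visible. If recording proves complete, the results do not change.
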